## 16. Efficacy Outcomes

### 16.1. PRIMARY EFFICACY

#### 16.1.1. PRIMARY EFFICACY VARIABLE & DERIVATION

The primary efficacy variable is the difference in Overall Response Rate (ORR) at Week 28, approximately 24 weeks after the completion of study treatment.

ORR is defined as the proportion of patients with complete response (CR) or partial response (PR) as assessed by central imaging review per IWG criteria 2007 until Week 28 after the start of treatment. ORR will be evaluated for each patient separately from the date of first administration of trial medication (i.e. Day 1) until either progression, death or up to Week 28 (i.e. study day 204 = 190+14), whichever happens earlier. Per protocol, CT scan (neck, chest, abdomen, pelvis, and any other areas known or suspected to be involved) with contrast to be conducted at screening, Week 12 and Week 28 (assessment permitted up to 4 weeks prior to, or 2 weeks after the Weeks 12 and 28 visit).

Patients who start subsequent anticancer therapy will typically have progressed or stopped treatment due to unacceptable toxicity. A CT scan should be conducted at their early treatment discontinuation visit. In the case where a patient starts subsequent anti-cancer therapy but the ORR evaluation period of that patient is still ongoing, the patient's ORR will be evaluated only until the start of subsequent anti-cancer therapy.

Unscheduled assessments recorded during the evaluation period for ORR will be taken into account for determination of ORR. Tumor assessments started on study day 204 but not completed on study day 204 will be fully included in the evaluation of best ORR.

The primary endpoint will be analyzed as described in section 16.1.3 and sensitivity analyses for the primary efficacy analysis will be performed as described in section 16.1.4.

---

Document:

Author:

Version Number:

Version Date:

Final v1.0

10Sep2019

Template No: CS\_TP\_BS016 Revision 4

Effective Date: 01Apr2016

Reference: CS\_WI\_BS005

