2.3 Study Endpoints

2.3.1 Primary Efficacy Endpoint

Overall Response Rate (ORR) (Complete Response [CR] + Partial Response [PR]) at Week 28, as defined by International Working Group (IWG) criteria 2007 (Appendix 4). This will be assessed centrally.

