8.8 Efficacy Analyses

The statistical analysis of the primary endpoint for this study will be performed after the last patient has completed the Week 28 response assessment. All efficacy data will be analyzed at this time, plus all PK, PD, immunogenicity, and safety data available at the time of data

cut-off, and these data will be reported in the CSR (Week 28 CSR). After the last patient has completed Week 52 of the study, a CSR addendum (Week 52 CSR) will be prepared to report the additional safety data.

Efficacy will be assessed centrally as CR, PR, SD, and PD, as defined in IWG criteria 2007, and TTE. The main efficacy endpoint will be the difference in ORR (CR+PR) at Week 28, approximately 24 weeks after the completion of study treatment. The efficacy analyses will be applied for both the PP set and FAS. FAS will be considered as primary efficacy analysis population and analysis in PP set will be conducted as a sensitivity analysis.

In FAS, patients without a response assessment at Week 28 will be handled using a conservative approach by imputation using drop-out reason (IUDR), where Non-responder imputation (NRI) method in case of treatment related reasons and otherwise multiple imputation (MI) procedure assuming missing at random (MAR) will be applied. For the PP set, all available data will be used for analysis.

Potential withdrawal reasons are considered as follows based on previous studies; The major reason of missing response assessment at Week 28 is assumed to be either the start of new treatment of FL due to lack of efficacy or toxicity based on Ardeshtna et al. In such reasons related to treatment (i.e. treatment failure requiring tumor targeting treatment for FL other than the protocol-defined treatment, death due to progressive disease), patients without a response assessment at Week 28 will be handled as non-responders. Missing responses unrelated to treatment (i.e. withdrawal by subject, pregnancy) as seen in the Colombat et al. would be considered ignorable missing at random (MAR) and multiple imputation procedure using logistic regression method will be used to impute the missing response assessment at Week 28 (responder versus non-responder). No imputation will be applied when the reasons are unknown whether they are related to treatment or not (i.e. lost to follow-up).

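### SAP 16.1.1 names the sole primary endpoint as response at Week 28 but derives it in words that permit best response up to Week 28

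*SAP*

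**What the plan says.** Protocol 2.3.1 sets the primary endpoint as "Overall Response Rate (ORR) (Complete Response [CR] + Partial Response [PR]) at Week 28, as defined by International Working Group (IWG) criteria 2007". Protocol 8.8 agrees: "The main efficacy endpoint will be the difference in ORR (CR+PR) at Week 28". Protocol 8.2 also places the hypothesis at Week 28.

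SAP 16.1.1 opens the same way: "The primary efficacy variable is the difference in Overall Response Rate (ORR) at Week 28". Its derivation then departs from this in five places:

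- ORR is the proportion with CR or PR "as assessed by central imaging review per IWG criteria 2007 until Week 28 after the start of treatment".
- Each patient is evaluated from Day 1 until progression, death or "up to Week 28 (i.e. study day 204 = 190+14), whichever happens earlier".
- "Unscheduled assessments recorded during the evaluation period for ORR will be taken into account for determination of ORR".
- Scans begun on Day 204 and finished later "will be fully included in the evaluation of best ORR".
- After new anti-cancer therapy, the patient's "ORR will be evaluated only until the start of subsequent anti-cancer therapy".

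SAP 16.1.2 (missing Week 28 assessments), SAP 16.1.3 (decision rule) and SAP Table 1 (imputation column) all work with status at Week 28. SAP 2.6 lists changes to the PK, PD and per-protocol sets and none to the primary endpoint. SAP 16.2.1 derives Week 12 ORR by reference to 16.1.1.

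**The concern.** Two programmers could follow SAP 16.1.1 in good faith and derive different values of the one variable that decides equivalence. The two readings part on patients who respond and then lose the response, or leave assessment, before Week 28.

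The difference bears on a biosimilarity claim. If SAIT101 responses were less durable than MabThera responses, Week 28 status would carry that into the equivalence test and best response would not. The loss would still show in the Week 28 response categories, the bar chart and time to event, but none of these decides equivalence. If the choice between readings were made after unblinding, either result could be challenged as selected.

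**Working it through.** **1. The plan's own figure.** Inputs from protocol 8.4: 154 per arm, 77% ORR in both arms, margin ±16.0 points, two-sided 95% Newcombe-Wilson CI. With p the observed proportion and (l, u) its Wilson limits, T for SAIT101 and C for MabThera:

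- lower = (pT − pC) − √[(pT − lT)² + (uC − pC)²]
- upper = (pT − pC) + √[(uT − pT)² + (pC − lC)²]

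Exact enumeration over two binomial arms gives 84.0% power, against 83% stated. The sample size is not in question. The calculations here are unstratified, while the planned CI is stratified by FLIPI-2, so they are approximate.

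**2. Patients who can be classed either way.**

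| Course | Best response up to Week 28 | Week 28 status |
|---|---|---|
| PR at Week 12, SD at Week 28 | Responder | Non-responder |
| CR/PR at Week 12, PD by Week 28 | Responder, unless the scan showing progression sets the status; 16.1.1 does not say | Non-responder if PD at Week 28 |
| CR/PR at Week 12, new FL therapy for lack of efficacy or toxicity, no Week 28 scan | Could be counted as responder | Non-responder (SAP 16.1.2, protocol 8.8) |
| CR/PR at Week 12, unrelated withdrawal | Could be counted as responder | Multiply imputed (16.1.2) |
| CR/PR at Week 12, lost to follow-up | Could be counted as responder | Not imputed (16.1.2) |

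The first row is possible under protocol Appendix 4. Take a single node, or nodes changing uniformly, with sum of products of diameters 100 at baseline, 45 at Week 12 and 60 at Week 28:

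- Week 12: (100 − 45)/100 = 55% decrease, so PR.
- Week 28: (100 − 60)/100 = 40% decrease, so not PR.
- From nadir: (60 − 45)/45 = 33% increase, so not PD.

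This patient never progresses, so stopping evaluation at progression does not settle the case.

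**3. How many patients would reverse a result.** Start from 119/154 (77.3%) in each arm on best response. Wilson limits for 119/154 are 70.0% to 83.2%.

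| SAIT101 vs MabThera | Lower 95% limit | Equivalent? |
|---|---|---|
| 119 vs 119 | −9.3% (upper +9.3%) | Yes |
| 110 vs 119 | −15.5% | Yes |
| 109 vs 119 | −16.1% | No |

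For 109 vs 119: −0.0649 − √[(0.7078 − 0.6316)² + (0.8318 − 0.7727)²] = −0.161. From parity, SAIT101 must lose 10 more responders than control (10/154 = 6.5% of the arm). The excess needed is still 10 if control itself loses 3, 5 or 8. If best response already stood at 110 vs 119, one further SAIT101 loss would reverse the result.

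**4. Chance of declaring equivalence when the true Week 28 ORR is 61% vs 77%** (difference at the margin). The losses between best response and Week 28 are assumed.

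| Points lost, SAIT101 / control | Best-response ORR | P(declare) |
|---|---|---|
| Week 28 status itself | 61% vs 77% | 2.7% |
| 3/3, 5/5 or 8/8 | 64/80, 66/82, 69/85 | 2.7% each |
| Equal proportion lost | 63.4/80, 65.0/82, 67.3/85 | 2.0%, 1.6%, 1.1% |
| 3/5 or 3/8 (control loses more) | 64/82, 64/85 | 1.0%, 0.2% |
| 5/3 | 66/80 | 6% |
| 8/3 | 69/80 | 18% |
| 10/3 | 71/80 | 31% |

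**5. Scan window.** From nominal Day 190, the protocol allowance of 4 weeks before to 2 weeks after gives Day 162 (190 − 28) to Day 204 (190 + 14). Counted from a visit at the late edge of its ±7-day window, the last day is 197 + 14 = 211.

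**The case against.** The best defence is that Week 28 status is plainly intended. It appears in protocol 2.3.1, 8.2 and 8.8, in the opening of SAP 16.1.1, and in 16.1.2, 16.1.3 and Table 1. Imputing a missing Week 28 assessment makes sense only for a fixed time point. SAP 2.6 is silent, and best ORR is mentioned once, in a sentence about scans that straddle Day 204. On this view the Day 204 text only describes a scan window.

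That is good evidence of intent, but the wording does not secure it. The protocol's Week 28 scan window opens four weeks before the visit. The SAP period opens on Day 1, closes at progression, takes in unscheduled scans and feeds a best response. A time-point endpoint needs none of these.

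Three parts of the defence do stand:

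- A reader might infer that new FL therapy is left undefined. It is not: protocol 8.8 and SAP 16.1.2 both make new therapy for lack of efficacy or toxicity, with no Week 28 assessment, non-response. What stays open is whether a scan taken just before that therapy counts as the Week 28 assessment.
- A reader might infer that the window is broadly contradictory. Protocol 5.1 schedules tumor assessments from Day 1, which supports a nominal Day 190 anchor, and SAP 6.4 is a data cut-off rule, not a responder rule. Only scans on Day 205 to 211 after a late in-window visit are unclear.
- Total tumor size alone does not exclude PD when nodes change unevenly, because Appendix 4 also tests single nodes. The worked example therefore needs one node or uniform change.

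**Conclusion.** The point holds as a contradiction within SAP 16.1.1, and between it and the protocol, on the only endpoint that decides equivalence. Followed as written, 16.1.1 can count a Week 12 PR with Week 28 SD as a responder. It should be corrected before unblinding.

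Two stronger conclusions are tempting and not supported. The first is that the sponsor has replaced the endpoint with best response: the text permits that reading, but the rest of the plan points the other way. The second is that the false-claim rate is inflated. The documents give no rates of lost response, so neither the number of affected patients nor the effect can be derived. The 6% to 31% range needs both a true difference at the margin and SAIT101 responses less durable by 2 to 7 points. With equal-point loss the rate stays at 2.7%, and with equal-proportion loss or greater control loss it falls. The case for correction rests on the two permitted derivations, not on a demonstrated error rate.

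**What to change.** Before unblinding:

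1. Rewrite SAP 16.1.1 so that a responder is a patient whose central-review status is CR or PR at the Week 28 assessment. Replace the whole sentence that runs evaluation from Day 1 to progression, death or Day 204, as well as the until-Week-28 and best-ORR phrases. Removing the two phrases alone would leave the cumulative rule in place.
2. State the Week 28 scan window once, with one anchor. Day 1 is supported by protocol 5.1 and gives Day 162 to 204. Say how a scan on Day 205 to 211 after a late in-window visit is treated, and how unscheduled scans inside and outside the window are used.
3. State how central-review PD before Week 28 is classed, and whether a pre-therapy scan counts as the Week 28 assessment. Otherwise keep the non-responder rule of SAP 16.1.2 and protocol 8.8.
4. Carry the same wording into Week 12 ORR in SAP 16.2.1.
5. Report best response up to Week 28, if at all, only as a labelled supportive analysis.

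The cost is SAP text, one derivation and at most one supportive table, with no new data. Observed ORR may be slightly lower than under best response. The stated power is unchanged, because the 77% planning rate is itself a month 7 rate.

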- g SAIT101 or MabThera[®] for i.v. infusion, 375 mg/m² body surface area.
- h Diagnostic biopsies will be reviewed locally and confirmed centrally in a retrospective manner. Patients can be entered based on a diagnosis of CD20+ follicular lymphoma reviewed at the investigational site. If a biopsy has not been performed within the previous 24 months prior to screening visit, a new biopsy is required to confirm that the histology is unchanged.
- i For patients who discontinue study drug early for any reason, and need to start a new treatment, Ann Arbor staging should be evaluated at their early treatment discontinuation visit.
- j To be reviewed locally and confirmed centrally. Patients with bone marrow biopsies demonstrating lymphoma within the previous year are not required to undergo a repeat bone marrow evaluation prior to study entry. Patients with a prior bone marrow biopsy performed more than 1 year before screening or negative for lymphoma will be required to undergo another bone marrow biopsy within 60 days prior to randomization. From Week 12 until EOS, a second bone marrow biopsy is required **only** if initially positive and to confirm CR based on the investigator's review of CT scan.
- k CT scan (neck, chest, abdomen, pelvis, and any other areas known or suspected to be involved) with contrast to be conducted at screening, Week 12 and Week 28 (assessment permitted up to 4 weeks prior to, or 2 weeks after the Weeks 12 and 28 visit). For patients who discontinue study drug early for any reason, and need to start a new treatment before the Week 28 visit, a CT scan should be conducted at their early treatment discontinuation visit. Brain scan (CT or MRI) can be conducted if CNS involvement is suspected.
For Investigators who routinely use PET scans for assessment of their patients, a PET scan may be performed **in addition to** (not instead of) the CT scan at the Investigator's discretion. Combined PET-CT scans may be used only if performed with contrast, and if the resolution is sufficient to allow accurate and consistent comparison of lesion measurements with subsequent CT scans. Where the contrast product is contraindicated, an abdomen-pelvic magnetic resonance imaging scan (MRI) should be performed with a non-contrast chest CT scan. An additional CT scan is recommended during the study if substantial progression is suspected, and mandated if treatment including chemotherapy or radiotherapy is to be started.

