5.1 Efficacy Assessments

Disease assessments are to be performed as scheduled according to calendar days, regardless of treatment delays resulting from toxicity. Care must be taken in scheduling disease assessments to prevent introduction of bias on treatment delays.

Assessments are NOT to be scheduled based on the previous visit time-point, but rather Day 1 should be used as baseline when calculating when the on-study tumor assessments are to be performed.

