2.1. Day 1 (Visit 2)

- Review inclusion/exclusion criteria to ensure patient eligibility
- Randomization via IXRS (can be conducted up to 4 days prior to Day 1).
- Note: Randomization will be stratified based on low, intermediate, and high risk patients using the Follicular Lymphoma International Prognostic Index 2 (FLIPI-2).

It is critical that the FLIPI-2 is scored correctly and that this information is entered into the IXRS accurately.

- IXRS study drug assignment.
- PE including body weight.
- Vital signs.
- Prior and concomitant medications.
- Adverse events.
- Laboratory testing including hematology, blood chemistry, urinalysis, serum β 2 microglobulin, and LDH.
- HBV DNA testing in patients with occult or prior hepatitis B infection (defined as positive total HBcAb and negative HBsAg) at screening.
- Urine pregnancy test for female patients of childbearing potential.
- PK / PD (CD19+ B-cell count) sampling at 0 hours (pre-dose), and at the end of infusion (\pm 10 minutes).
- IgG and IgM sampling.
- Immunogenicity sampling prior to dosing.
- Administration of pre-medications.
- Study drug administration.

2.2. Treatment Visits (Visits 3, 4, and 5 – Study Days 8, 15 and 22)

- PE including body weight.
- Vital signs.
- Concomitant medications.
- Adverse events.
- Laboratory testing including hematology, blood chemistry, and urinalysis.
- PK / PD (CD19+ B-cell count) sampling at 0 hours (pre-dose), and at the end of infusion (\pm 10 minutes)
- IgG and IgM sampling
- Immunogenicity sampling prior to dosing (Day 15 only).
- Contact IXRS.

- Administration of pre-medications.
- Study drug administration.

2.3. Follow-up Visits (Visit 6, 7, 8, 9 and 10 –Weeks 5, 12, 20, 28 and 36)

- Physical examination (PE).
- Vital signs.
- ECOG performance status assessment (Weeks 5 and 28 only).
- 12-lead ECG (Week 28 only).
- Concomitant medications.
- Adverse events.
- Laboratory testing including hematology, blood chemistry, urinalysis, serum β 2 microglobulin, and LDH.
- HBV DNA testing in patients with occult or prior hepatitis B infection (defined as positive total HBcAb and negative HBsAg) at screening.
- Ann Arbor staging (Week 28 only).
- Contrast enhanced CT scan of neck, chest, abdomen and pelvis, and any other areas known or suspected to be involved. Assessment permitted up to 4 weeks prior to, or 2 weeks after the Week 28 visit. Optional PET or PET-CT scan in addition to CT scan. MRI where the contrast product is contraindicated. (Weeks 12 and 28)

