#### **5.1. STUDY DAY**

Study Day in days will be calculated from the date of the first study drug administration (Day 1) and will be used to show the start/stop day of assessment or event.

If the date of the event is on or after the first study drug date then:

- Study Day = date of event – first study drug date + 1.

If the date of the event is prior to the first study drug date, then:

- Study Day = date of event – first study drug date.

In the situation where the event date is partial or missing, the date will appear partial or

---

Document:

Author:

Version Number:

Version Date:

Final v1.0

10Sep2019

Template No: CS\_TP\_BS016 Revision 4

Effective Date: 01Apr2016

Reference: CS\_WI\_BS005

missing in the listings and Study Day will be calculated after proper imputation has been carried out as described in APPENDIX 1.

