### **6.4. DATA EXTRACTION RULE**

For the Week 28 CSR, only data up to the target visit will be included for reporting purpose. For example, at the Week 28 CSR, the cut-off date will be each patient's last assessment date at the Week 28 visit (or date of withdrawal if withdrawn before Week 28) or CT scans within 14 days, whichever comes last. For example, if one patient had CT scans 10 days after their Week 28 visit, his/her cut-off date will be the date of Week 28 visit+10; if a patient didn't have CT scans within 14 days of their Week 28 visit, his/her cut-off date will be the last assessment date of the Week 28 visit. The cut-off date for each patient may be different. Specific data extraction rules are described in Appendix 2.

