## 16.2. SECONDARY EFFICACY

### 16.2.1. SECONDARY EFFICACY VARIABLE(S) & DERIVATION(S)

#### ORR at Week 12

The Overall Response Rate (ORR) at Week 12 will be derived as described in section 16.1.1, i.e., similar to the primary endpoint (ORR at Week 28).

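### SAP 16.1.1 ends the primary ORR window at fixed Day 204, so Week 28 CT scans that the protocol permits after a late in-window visit (up to Day 211) fall outside the primary endpoint

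*SAP*

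**What the plan says.** - **Visit window.** Protocol Table 1 (section 3.1) places the Week 28 visit at Day 190 with a window of 7 days either side, and the Week 12 visit at Day 78 with 3 days either side.
- **Scan allowance.** Footnote k to that table has the CT "assessment permitted up to 4 weeks prior to, or 2 weeks after the Weeks 12 and 28 visit". Protocol Appendix 10, in the list for the follow-up visits, agrees: "Assessment permitted up to 4 weeks prior to, or 2 weeks after the Week 28 visit". Both count from the visit.
- **Primary endpoint window.** SAP 16.1.1 evaluates ORR from the first dose "until either progression, death or up to Week 28 (i.e. study day 204 = 190+14), whichever happens earlier". It repeats the protocol's visit-based scan allowance in the same paragraph. Its only exception to the end day is this: "Tumor assessments started on study day 204 but not completed on study day 204 will be fully included in the evaluation of best ORR".
- **Data cut.** SAP 6.4 works from each patient's own visit: "if one patient had CT scans 10 days after their Week 28 visit, his/her cut-off date will be the date of Week 28 visit+10". If no CT falls within 14 days of the visit, the cut-off is the last assessment date of the visit itself.
- **Week 12.** SAP 16.2.1 carries the derivation over: "The Overall Response Rate (ORR) at Week 12 will be derived as described in section 16.1.1".
- **Declared changes.** SAP 2.6, which lists departures from the protocol, does not mention a narrower scan window.

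**The concern.** Day 204 is the nominal visit day plus the scan allowance, with the visit window left out. A patient seen late but within the window, and scanned late but within the allowance, has followed the protocol, yet the planned Week 28 scan is not used for the sole primary endpoint. SAP 16.1.1 and 6.4 also give programmers two different end points for what should be one set of scans. If that is settled only after unblinding, the choice can look data-driven.

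The lost scan has two possible consequences, and the SAP does not say which applies:

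- The patient is classified on an earlier scan, such as Week 12. SAP 16.1.1 evaluates from Day 1 and speaks of a best response, which allows this.
- The patient is treated as having no Week 28 response. SAP 16.1.2 has no clear rule for a scan that exists but is late. One line scores missing or non-evaluable assessments as non-response, another calls for multiple imputation, and a third for no imputation, depending on the reason.

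In either case, progression first documented on that scan does not change ORR. It does count as an event for TTE, which has no Day 204 limit (SAP 16.2.1, Table 2).

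**Working it through.** **Inputs.** Week 28 visit: Day 190 ± 7 (Protocol Table 1). CT allowance: up to 14 days after the visit and up to 28 days before it (footnote k, Appendix 10). End of ORR window: Day 204 (SAP 16.1.1). Study Day 1 is the first dose (SAP 5.1).

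**1. The SAP's figure.** Nominal Week 28 day = 27 × 7 + 1 = 190, and 190 + 14 = 204. This reproduces exactly, without the ±7.

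**2. Latest scan the protocol permits.** 190 + 7 + 14 = Day 211, so Days 205 to 211 are at issue.

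**3. Gap by visit day.** Gap = (visit day + 14) − 204 = visit day − 190, where positive.

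| Week 28 visit | Last permitted scan | Days lost |
|---|---|---|
| Day 183 to 190 | Day 197 to 204 | 0 |
| Day 191 | Day 205 | 1 |
| Day 194 | Day 208 | 4 |
| Day 197 | Day 211 | 7 |

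**4. SAP 16.1.1 against SAP 6.4.**

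- Visit Day 196, CT Day 206: the scan is 10 days after the visit. It is permitted and inside the 6.4 data cut, but outside the ORR window.
- Visit Day 183, CT Day 200: the scan is 17 days after the visit. It is inside the ORR window, but 6.4 finds no CT within 14 days and cuts off at the visit.

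The rules disagree in both directions.

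**5. Possible share of scans.** The documents give no distribution of scan dates. As an illustration, assume visits are uniform over the 15 days 183 to 197 and scans uniform over the 43 days from −28 to +14. There are 15 × 43 = 645 combinations. Those after Day 204 number 1 + 2 + … + 7 = 28, and 28/645 = 4.3%.

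**6. Possible effect on power.** This is also illustrative. Exact enumeration of the unstratified Newcombe-Wilson 95% interval (154 per arm, 77% in both arms, margin ±16 points) gives power 0.840, against the stated 83%. With equal losses in both arms:

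| Share affected (assumed) | Patients left out | All scored non-responders |
|---|---|---|
| 2% | 0.827 | 0.818 |
| 5% | 0.810 | 0.786 |

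The right-hand column is the worst case. If affected patients keep a response from an earlier scan, the loss is smaller than either column suggests.

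**7. Week 12.** The latest permitted scan is 78 + 3 + 14 = Day 95. Applying the 16.1.1 formula by analogy would give 78 + 14 = Day 92, but the SAP states no such day.

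**The case against.** The strongest counter-reading is that Day 204 is intended. Protocol 5.1 says that "Day 1 should be used as baseline when calculating when the on-study tumor assessments are to be performed", which could support counting two weeks from nominal Day 190, and a common fixed end day is a legitimate choice for a response endpoint. This has some force. But footnote k, Appendix 10 and the SAP's own restatement all count from the visit, the example in SAP 6.4 uses the patient's actual visit date, and SAP 2.6 declares no change. The visit-based reading is better supported.

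It can also be said that SAP 6.4 is an extraction rule and not an endpoint definition, and that TTE may properly count an event that a Week 28 response does not. Both points are fair. They make the mismatch less of a formal contradiction, but they do not explain why a compliant scan should be extracted and then left unused for ORR.

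A reader might go further and infer that affected patients drop out of the primary endpoint, or become non-responders, and that the equivalence test is biased. The documents do not support that. The scan is lost, not necessarily the patient, because an earlier CR or PR may still count. The test is on the difference between arms, sites and patients are blinded (Protocol 4.10), and nothing suggests that late scans would be more common in one arm. The sensitivity analyses in SAP Table 1 (no imputation, NRI, MI, PPS) would also show part of the effect if late scans became missing responses. They would not restore the scans.

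**Conclusion.** The mismatch stands. For Week 28 visits on Days 191 to 197, scans that the protocol permits can fall 1 to 7 days after the SAP closes the ORR window. The full 7 days apply only to a Day 197 visit, and visits up to Day 190 lose nothing. This rests on reading the scan allowance as running from the patient's actual visit.

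The number of patients affected and any difference between arms cannot be determined from the documents. The effect is probably small: the 4.3% share is a uniform-timing illustration, and the power figures depend on assumed shares and on how a late scan is handled. The case for acting is that the window of the only primary endpoint should be unambiguous before unblinding and should not discard scans that the protocol allows. It does not rest on a demonstrated bias. For Week 12, the point is only that the SAP states no end day and refers back to a formula that omits the visit window.

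**What to change.** Before unblinding:

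1. In SAP 16.1.1, end the ORR window at the later of Day 204 and the actual Week 28 visit date + 14 days (in-window maximum Day 211). A common Day 211 for all patients is an acceptable alternative. Leave the earlier stops for progression, death and new anti-cancer therapy unchanged.
2. Align SAP 6.4 so that the Week 28 cut extracts the same scans that 16.1.1 evaluates.
3. In SAP 16.2.1, state the matching visit-based limit for Week 12 (in-window maximum Day 95).

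A limit of actual visit + 14 days alone would not do. For visits on Days 183 to 189 it would end on Days 197 to 203 and exclude scans up to Day 204 that the present rule counts.

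If the sponsor does intend Day 204, it should be listed in SAP 2.6 as a change from the protocol, with an explicit rule for compliant scans taken later.

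The cost is a few lines of SAP text and one derivation rule, with no new data. The downside is that a few responses are read up to a week later.
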